11.3. Clinical Laboratory Evaluations

The endpoints for clinical laboratory evaluations include:

- Laboratory marked abnormalities (see Appendix A2)
- Observed value and change from baseline over time in the following laboratory parameters including but not limited to
 - Complete blood count: red blood cell [RBC] count, hemoglobin, hematocrit, white blood cell [WBC] count and differential, absolute WBC counts, platelet count
 - Serum chemistry: total protein, albumin, calcium, phosphorous, glucose, total cholesterol [TC], triglycerides, high-density lipoprotein [HDL], high-density lipoprotein cholesterol [HDL-C], low-density lipoprotein cholesterol [LDL-C], uric

acid, total bilirubin, alkaline phosphatase, aspartate aminotransferase [AST; serum glutamic-oxaloacetic transaminase, SGOT], alanine aminotransferase [ALT; serum glutamic pyruvic transaminase, SGPT], sodium, potassium, chloride, bicarbonate [carbon dioxide, CO₂], blood urea nitrogen, creatinine, lactate dehydrogenase [LDH], and magnesium

- Dipstick urinalysis: specific gravity, pH, glucose, ketones, protein, blood, bilirubin, leukocyte esterase, nitrite, and urobilinogen
- Shifts from baseline to post-baseline time points and to the worst post-baseline value in terms of normal/abnormal (low or high) in the above hematology and serum chemistry parameters

Summary statistics of observed values and changes from baseline in laboratory parameters will be provided over time. Frequency summaries (shift tables) of shifts from baseline to post-baseline time points and to the worst post-baseline value in terms of normal/abnormal will be provided.

Laboratory marked abnormalities will be summarized; subject incidence and EAIR for each abnormality will be calculated based on subjects with a baseline value and at least one post-baseline value for criteria requiring baseline or subjects with at least one post-baseline value for criteria not requiring baseline. A subject data listing of laboratory marked abnormalities will be provided. Laboratory marked abnormalities will also be summarized for subjects with normal values at baseline and for subjects with abnormal values at baseline separately. For the purposes of these summaries, subjects with abnormal (normal) values at baseline are defined as those whose baseline value is low (not low) for criteria concerning low values and those whose baseline value is high (not high) for criteria concerning high values; both low and high are relative to the laboratory normal range.

A subject data listing of all laboratory data, including urinalysis, will be provided.

11.4. Columbia Suicide Severity Rating Scale (C-SSRS)

All subjects will complete the Columbia-Suicide Severity Rating Scale (C-SSRS) assessment at all study visits. C-SSRS is a scale that captures the occurrence, severity, and frequency of suicide-related ideations and behaviors during the assessment period (Posner, 2007). At Visit 1 (Screening) the C-SSRS will be completed for the subject's lifetime history of suicidal ideation and behavior. At all other visits the C-SSRS will be completed for ideation and behavior since the previous visit.

A summary and subject data listing of psychiatric evaluation results will be provided.

APPENDIX A1 – CONVENTIONS RELATED TO DATES

Following are the general conventions for various computations and imputations for references. Users may need to consult with study team for specific study practices or regulatory guidelines.

11.5. A1.1 Guideline of Partially Missing Date Imputation

A1.1.1 Adverse Events

Partially missing AE start dates will be imputed in the ADaM dataset for AEs, but partially missing AE end dates will not be imputed in the same dataset. If the AE end date is complete with no missing year, month, or day, and the partially missing start date imputed by the rules below is after the AE end date, then the start date will be imputed by the AE end date.

Subjects who were treated with apremilast at Week 0/Visit 2

The principle of the imputation rules for subjects who were treated with apremilast initially is to treat the AE as treatment-emergent, i.e., occurring on or after the date of the first dose of IP, if possible.

Let an AE start date be represented as " $D_{Event}/M_{Event}/Y_{Event}$ ", and the date of the first dose of IP as " $D_{IP}/M_{IP}/Y_{IP}$ ". The following table gives the imputation rules for partially missing AE start dates for subjects who were treated with apremilast initially.

Table 4: Imputation Rules for Partially Missing AE Start Dates for Subjects Who Were Treated with Apremilast Initially

Scenario	Condition	Imputation Rule		
Partially missing date includes year only (both month and day are missing)				
1	$Y_{Event} < Y_{IP}$	12/31/Y _{Event}		
2	Otherwise, i.e., $Y_{IP} \le Y_{Event}$	Max (date of first dose of IP, 1/1/Y _{Event})		
Partially missing date includes both year and month (only day is missing)				
1	$Y_{Event} < Y_{IP}$, or $(Y_{Event} = Y_{IP} \text{ and } M_{Event} < M_{IP})$	Last date of M _{Event} /Y _{Event}		
2	Otherwise, i.e., $Y_{IP} < Y_{Event}$, or $(Y_{IP} = Y_{Event})$ and $M_{IP} \le M_{Event}$)	Max (date of first dose of IP, 1/M _{Event} /Y _{Event})		

Subjects who were treated with placebo at Week 0/Visit 2

The principle of the imputation rules for subjects who were treated with placebo initially and started apremilast treatment at Week 16 is to consider the AE starting on or after the date of the first dose of apremilast, if possible; if the partially missing start date suggests that it is prior to the date of the first dose of apremilast, the AE will be considered starting on or after the date of the first dose of IP, if possible.

The following are 4 scenarios considered in the imputation rules:

1. The partially missing AE start date suggests the date is prior to the date of the first dose of IP: impute it by the latest possible date (determined by the non-missing field of the date);

- 2. The partially missing AE start date suggests the date is after the date of the first dose of apremilast following Week 16: impute it by the earliest possible date (determined by the non-missing field of the date);
- 3. The partially missing AE start date is in the same year (if both month and day are missing), or the same year/month (if only day is missing) of the first dose of apremilast following Week 16: impute it by the date of the first dose of apremilast;
- 4. The partially missing AE start date suggests the date is no earlier than the date of the first dose of IP but prior to the date of the first dose of apremilast following Week 16: impute it by the date of the first dose of IP, or the earliest possible date (determined by the non-missing field of the date), whichever occurs later.

Let an AE start date be represented as " $D_{Event}/M_{Event}/Y_{Event}$ ", the date of the first dose of IP as " $D_{IP}/M_{IP}/Y_{IP}$ ", and the date of the first dose of apremilast following Week 16 as " $D_{APR}/M_{APR}/Y_{APR}$ ". The following table gives the imputation rules for partially missing AE start dates.

Table 5: Imputation Rules for Partially Missing AE Start Dates for Subjects Who Were Treated with Placebo Initially

Scenario	Condition	Imputation Rule			
Partially r	missing date includes year only (both month and d	lay are missing)			
1	$Y_{Event} < Y_{IP}$	12/31/Y _{Event}			
2	$Y_{Event} > Y_{APR}$	1/1/Y _{Event}			
3	$Y_{Event} = Y_{APR}$	Date of first dose of apremilast following Week 16			
4	Otherwise, i.e., $Y_{IP} \le Y_{Event} < Y_{APR}$	Max (date of first dose of IP, 1/1/Y _{Event})			
Partially r	missing date includes both year and month (only d	lay is missing)			
1	$Y_{Event} < Y_{IP}$, or $(Y_{Event} = Y_{IP} \text{ and } M_{Event} < M_{IP})$	Last date of M _{Event} /Y _{Event}			
2	$Y_{Event} > Y_{APR}$, or $(Y_{Event} = Y_{APR} \text{ and } M_{Event} > M_{APR})$	1/M _{Event} /Y _{Event}			
3	$Y_{Event} = Y_{APR}$ and $M_{Event} = M_{APR}$	Date of first dose of apremilast following Week 16			
4	Otherwise, i.e., Y _{IP} < Y _{Event} < Y _{APR} , or	Max (date of first dose of IP, 1/M _{Event} /Y _{Event})			
	$(Y_{IP} = Y_{Event} < Y_{APR} \text{ and } M_{IP} \le M_{Event}), \text{ or}$				
	$ (Y_{IP} = Y_{Event} = Y_{APR} \text{ and } M_{IP} \le M_{Event} \le M_{APR}), $ or $(Y_{IP} \le Y_{Event} = Y_{APR} \text{ and } M_{Event} \le M_{APR})$				

A1.1.2 Prior/Concomitant Medications/Procedures

Partially missing start/stop dates for prior/concomitant medications and partially missing start dates for prior/concomitant procedures will be imputed in the ADaM dataset for prior/concomitant medications/procedures. For prior/concomitant medications, if the stop date is complete with no missing year, month, or day, and the partially missing start date imputed by the rule below is after the stop date, then the start date will be imputed by the stop date.

Partially missing prior/concomitant medication/procedure start dates will be imputed by the earliest possible date given the non-missing field(s) of the date.

Partially missing prior/concomitant medication stop dates will be imputed by the latest possible date given the non-missing field(s) of the date. If the imputed start date is after the stop date, the start date will be imputed as the stop date -1.

A.1.1.3 Medical History

Partially missing medical history start dates will be imputed in the ADaM dataset for medical history (for the purposes of calculating durations of PsA and psoriasis). The 16th of the month will be used to impute a partially missing start date that has only the day missing, and July 1st will be used to impute a partially missing start date that has both the month and day missing.

If the imputed start date is after the stop date, the start date will be imputed as the stop date -1.

A1.1.4 Treatment Duration

Partially or completely missing last dose dates will be imputed in the ADaM dataset for treatment duration.

When partially missing last dose date is available, set last dose date to the maximum of [the earliest possible date given the non-missing field(s) of last dose date, the minimum of (the latest possible date given the non-missing field(s) of last dose date, last known date in database, first non-missing Early Termination (ET) visit date)]

When last dose date is completely missing, set last dose date to the minimum of (last known date in database, first non-missing Early Termination (ET) visit date)

Last known date in database is defined as maximum of (last visit date, lab, vital signs, ECG assessment date, AE start or end dates, concomitant medications start or end dates, concomitant procedure date, last dose date from 'Disposition- Treatment' page, treatment exposure start or end dates where doses were completely or partially taken, death date).

APPENDIX A2 – LABORATORY MARKED ABNORMALITIES CRITERIA

Table 6: Laboratory Marked Abnormalities Criteria

Category / Analyte	SI Units	Criteria
Chemistry/	U/L	> 2*ULN
Alanine Aminotransferase (SGPT)		
Albumin	Kg/m3	< 25
Alkaline Phosphatase	U/L	> 400
Aspartate Aminotransferase (SGOT)	U/L	> 2*ULN
Total Bilirubin	μmol/L	> 2*ULN
Total Bilirubin and Alanine	μmol/L and	Bilirubin Value > 2xULN with (ALT
Aminotransferase /Aspartate	U/L	or AST value > 2xULN)
Aminotransferase		
Blood Urea Nitrogen	mmol/L	> 24
Calcium	mmol/L	< 1.8
		> 3.0
Cholesterol	mmol/L	> 7.8
Creatinine	μmol/L	> 1.5*ULN
Glucose	mmol/L	< 2.8
		> 13.9
Hemoglobin A1C	%	> 6.5
Lactate Dehydrogenase (LDH)	U/L	> 2*ULN
Magnesium	mmol/L	> 1.2
Phosphate	mmol/L	<1.03
		>1.94
Potassium	mmol/L	<3.0
		>5.4
Sodium	mmol/L	<132
		>147
Triglycerides	mmol/L	> 3.4

Urate	umol/L	Male: > 480 Female: > 480
Hematology/		
Hemoglobin	g/L	Female <110, Male <110
		Female >150, Male >150
Leukocytes	10^9/L	< 2.0
Lymphocytes	10^9/L	< 1.0
Neutrophils	10^9/L	< 1.5
Platelets	10^9/L	<100
		>500

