#### 4.2. Inclusion Criteria

Subjects must satisfy the following criteria to be enrolled in the study:

- 1. Subject must be male or female, ≥18 years of age at the time of signing the informed consent form (ICF).
- 2. Subject must understand and voluntarily sign an ICF prior to any study-related assessments / procedures being conducted.
- 3. Subject is willing and able to adhere to the study visit schedule and other protocol requirements.
- 4. Subject must have a diagnosis of chronic plaque psoriasis for at least 6 months prior to signing the ICF.
- 5. Subject must have a diagnosis of mild to moderate plaque psoriasis at both Screening and Baseline as defined by:
  - a. sPGA score of 2-3 (mild to moderate)
  - b. BSA 2-15%
  - c. PASI score 2-15
- 6. Subject must be inadequately controlled with, or intolerant of at least one topical therapy (including topical corticosteroids, topical retinoids or vitamin D analog preparations, calcipotriene and betamethasone dipropionate ointment or foam, tacrolimus, pimecrolimus, or anthralin/dithranol) for the treatment of psoriasis at both Screening and Baseline.
- 7. Subject has not had prior exposure to biologics for the treatment of psoriatic arthritis, psoriasis, or any other indication that could impact the assessment of psoriasis.
- 8. Subject must be in good health (except for psoriasis) as judged by the investigator, based on medical history, physical examination, clinical laboratories, and urinalysis.
- 9. Subject must meet the following laboratory criteria:
  - a. White blood cell count  $\ge 3000/\text{mm}^3 \ (\ge 3.0 \times 10^9/\text{L})$  and  $< 14,000/\text{mm}^3 \ (< 14 \times 10^9/\text{L})$
  - b. Platelet count  $> 100.000/\mu L$  ( $> 100 \times 109/L$ )
  - c. Serum creatinine  $\leq 1.5 \text{ mg/dL}$  ( $\leq 132.6 \mu \text{mol/L}$ )
  - d. Aspartate aminotransferase (AST) (serum glutamic oxaloacetic transaminase [SGOT]) and alanine aminotransferase (ALT) (serum glutamic pyruvic transaminase [SGPT])  $\leq 2$  x upper limit of normal (ULN)
  - e. Total bilirubin  $\leq 2 \text{ mg/dL } (34 \mu\text{mol/L})$

10. Females of childbearing potential (FCBP) must have a negative pregnancy test at Screening and Baseline. While on investigational product and for at least 28 days after taking the last dose of investigational product, FCBP who engage in activity in which conception is possible must use one of the approved contraceptive options described below:

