11. SAFETY ANALYSIS

Safety will be assessed via descriptive statistics. Unless otherwise specified, all safety analyses described in this section will be performed for both the Placebo-controlled Phase and the Apremilast-exposure Period. The safety analyses for the Placebo-controlled Phase will be based on the safety population and presented by treatment group (placebo arm or apremilast arm), and the safety analyses for the Apremilast-exposure Period will be based on the apremilast subjects as treated population and presented by treatment group (Placebo/30 mg BID, 30 mg BID as Initiated and 30 mg BID as Treated).

For the analyses of AEs and lab marked abnormalities, the following endpoints will also be summarized:

- Subject incidence: Subject incidence (i.e., percentage [%] used in a frequency summary) is defined as the number of subjects with the specific event divided by the number of subjects included in the analysis. Subjects with multiple occurrences of the specific event in the specific analysis period will be counted only once in the numerator.
- Exposure-adjusted incidence rate (EAIR) per 100 subject-years: The EAIR per 100 subject-years is defined as 100 times the number of subjects with the specific event divided by the total exposure time (in years) among subjects included in the analysis. Subjects with multiple occurrences of the specific event in the specific analysis period will be counted only once in the numerator. The exposure time for a subject without the specific event is the treatment duration, whereas the exposure time for a subject with the specific event is the treatment duration up to the start date (inclusive) of the first occurrence of the specific event. The total exposure time in years is calculated by dividing the sum of exposure time in days over all subjects included in the analysis by 365.25. The EAIR per 100 subject-years is interpreted as the expected number of subjects with at least one occurrence of the specific event per 100 subject-years of exposure to the IP.

AEs and lab marked abnormalities will be summarized by subject incidence and EAIR for the Placebo-controlled Phase (Weeks 0 to 16) and for the Apremilast-exposure Period. In addition, selected summaries for the Apremilast Extension Phase (Weeks 16 to 32) and the Observational Follow-up Phase (4 weeks) may be presented if deemed necessary.

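### SAP Table 6 sets one high haemoglobin limit, 150 g/L, for men and women without a rationale, so the row may flag many unremarkable male values

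*SAP*

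**What the plan says.** SAP Appendix A2, Table 6 lists the criteria for a marked laboratory abnormality. The haemoglobin row (g/L) has separate entries for women and men, but the values are equal. The upper limit is "Female >150, Male >150" and the lower limit is "Female <110, Male <110". The urate row has the same pattern: "Male: > 480 Female: > 480". No reason is given for naming the sexes and then treating them alike.

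The rules that turn a value into a count are these:

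- **Denominator (SAP 11.3).** Where a criterion does not involve baseline, incidence and exposure-adjusted incidence rate (EAIR) are based on "subjects with at least one post-baseline value for criteria not requiring baseline". The haemoglobin criterion is of this kind.
- **Counting (SAP 11).** "Subjects with multiple occurrences of the specific event in the specific analysis period will be counted only once in the numerator". One value above the limit at any visit in the period is therefore enough. For the EAIR, that subject's exposure time stops at the first such value.
- **Baseline split (SAP 11.3).** "Laboratory marked abnormalities will also be summarized for subjects with normal values at baseline", and separately for those with abnormal values. For this split, "both low and high are relative to the laboratory normal range".

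Protocol 4.2 enrols both sexes ("Subject must be male or female") and requires good health apart from psoriasis. Its list of laboratory criteria contains no haemoglobin limit. Protocol Table 3 schedules post-baseline laboratory tests at Weeks 8 and 16 in the placebo-controlled phase, and at Weeks 24 and 32 in the extension.

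**The concern.** A row divided by sex with the same number in both halves looks like a template entry that was never completed. The liver enzyme, bilirubin, creatinine and LDH rows of the same table are tied to the laboratory's upper limit of normal (ULN). The haemoglobin limit is a fixed number with no stated link to any range.

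If 150 g/L lies inside the ordinary male range, the row counts men whose haemoglobin is unremarkable and has not moved. The baseline split does not remove them, because it uses a different yardstick. Suppose the laboratory's male upper limit is above 150 g/L. A man who stays between 150 and that limit throughout is normal at baseline by the laboratory range and markedly abnormal by Table 6 on the same value. The normal-at-baseline summary, which a reader would take to show new abnormalities, would then include men with no change.

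What is at stake is the interpretability of one safety row: its incidence, its EAIR and the accompanying subject listing.

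**Working it through.** **No figure to reproduce.** The 150 g/L limit is a chosen threshold with no derivation in the documents. The question is what share of men it would flag.

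**Inputs from the documents.** Limit >150 g/L for both sexes (SAP Table 6); one value is enough (SAP 11 and 11.3); two scheduled post-baseline samples in the placebo-controlled phase, Weeks 8 and 16 (Protocol Table 3); about 287 subjects per arm (SAP 4.4).

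**Assumed inputs.** The documents give no haemoglobin mean, SD, within-subject correlation, sex mix or laboratory range. I assume a normal distribution in men, mean 140 to 155 g/L, SD 9 to 12, and correlation 0.7 between visits. Values are taken as whole g/L, so >150 is cut at 150.5.

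**Step 1: one sample.** Share flagged = 1 − Φ((150.5 − mean)/SD).

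- Mean 140, SD 9: z = 10.5/9 = 1.17, share 12%.
- Mean 145, SD 12: z = 5.5/12 = 0.46, share 32%.
- Mean 150, SD 9 to 12: z = 0.06 to 0.04, share 48%.
- Mean 155, SD 9: z = −4.5/9 = −0.50, share 69%.

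The range is 12% to 69%.

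**Step 2: at least one of two samples.** Share = 1 − Φ₂(z, z; ρ), where Φ₂ is the bivariate normal distribution function. With ρ = 0.7 it is 18% at mean 140, SD 9, and 80% at mean 155, SD 9. With ρ = 0.9 the same two cases give 16% and 76%.

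**Step 3: where the concern fades.** At a lower male mean of 135, cutting at 150 exactly, the single-sample share is 1 − Φ(15/8) = 3% for SD 8 and 1 − Φ(15/12) = 11% for SD 12. To flag no more than 5% of men per sample, the mean must be at or below 150 − 1.645 × SD, which is about 137 for SD 8 and 130 for SD 12.

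**Step 4: effect on the row.** Assume further that 50% to 70% of subjects are men, that 30% to 70% of men and 2% of women are flagged, and that all 287 per arm contribute. The background per arm is then

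- low end: 0.5 × 0.30 + 0.5 × 0.02 = 0.16;
- high end: 0.7 × 0.70 + 0.3 × 0.02 = 0.496.

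The 95% CI half-width for the arm difference is 1.96 × √(2b(1 − b)/287). This gives 6.0 points at b = 0.16 and 8.2 points at b = 0.496, against 1.6 points at b = 0.01. The SAP plans no such interval; it is shown only to measure the noise.

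**The case against.** The strongest reply has five parts.

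- **No data.** The documents contain no haemoglobin distribution and no laboratory range. A reader might infer that the limit flags a large share of men whatever their distribution. The documents do not support that, and at a mean of 135 the share is 3% to 11%. The mismatch with the baseline split likewise arises only if the male upper limit exceeds 150 g/L. Both conditions stand and are part of the conclusion.
- **Other displays exist.** A reader might infer that the row is worthless or conceals a real effect. It does not go that far. The row is shown by arm against concurrent placebo, so the comparison remains possible. SAP 11.3 also plans haemoglobin values and changes over time, shift tables by visit and to the worst value, and a full listing. Protocol 9.7 refers the laboratory shift tables to the normal reference ranges.
- **No overall count.** A reader might infer that the total number of marked abnormalities is inflated. SAP 11.3 specifies summaries for each abnormality and describes no pooled count.
- **Fixed limits are usual in Table 6.** Only the ALT, AST, bilirubin, combined bilirubin and transaminase, creatinine and LDH rows use the ULN; the other 18 analytes have fixed limits. The identical-by-sex layout recurs for urate and may be a formatting convention. So the layout alone does not prove an error. It does leave the choice unexplained.
- **No rarity standard.** The SAP does not say how uncommon a marked abnormality should be. That is true, but a limit met by a large minority or a majority of men would not match the word.

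**Conclusion.** The concern holds in limited form and is minor. What is certain is that Table 6 applies one upper haemoglobin limit to both sexes in a row laid out by sex, without a rationale, without a change-from-baseline element, and with a single value sufficient to count a subject.

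The size is conditional. On the assumed male means and SDs, between about one man in eight and two in three would be flagged on one sample, and up to four in five over the two placebo-phase visits. A male mean near 135 would make the problem small. Within the higher range, the row's incidence and EAIR would be non-specific and noisy in both arms. If the male upper limit is above 150 g/L, the normal-at-baseline split would not repair this.

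The effect stops at one descriptive safety row and its listing. Protocol 9.7 plans no inferential safety testing, and no efficacy analysis uses this criterion.

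**What to change.** Before the Week 16 unblinding, by which time SAP section 2 requires the plan to be final and signed:

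1. Replace the common 150 g/L with separate limits for men and women, each defined relative to the central laboratory's sex-specific ULN. The ALT, AST, bilirubin, creatinine and LDH rows already work relative to the ULN.
2. State the multiple or margin. A limit set at the ULN itself would largely repeat the planned shift tables.
3. Check the low haemoglobin limit (<110 g/L) and the urate limit (>480 µmol/L), also identical by sex, against the same laboratory's ranges. Correct them or record why one value serves both sexes.

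The cost is a small edit to one SAP table and its programming. Fewer subjects will be flagged as high. Made before unblinding, the change cannot be read as prompted by the data.
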